We will use a randomized, controlled pilot study design in which 60 adults with T2D are randomized to the Yo Puedo + mHealth or wait-list control condition with the hypothesis that clinical (A1C, BMI, BP), T2D self-management, and self-efficacy outcomes will be greater in Yo Puedo + mHealth participants compared to the wait-list control condition at 3 and 6 month follow-up. We also hypothesize that the Yo Puedo + mHealth program is feasible and acceptable to adults with T2D and providers, and that fidelity of the program will be maintained. Those in the control group will be invited to participate in the program after completion of the 6-month data collection. We will reconsent control group participants who chose to participate in the program after the 6-month data collection to have data collected one more time, approximately 3 months after the first class. Participants will be consented for this additional data collection in person at the last session of classes or prior to the data collection session itself. We will conduct interviews with the program instructors, participants, and select clinic personnel to identify barriers, facilitators, and acceptability of the program from multiple perspectives, recognizing the complexity of the health care system. Detailed notes on the process of implementation will be carefully recorded with the purpose of identifying successful and unsuccessful components of the program (positive and negative feedback loops in a complex system).

Setting. The study will be conducted in up to 10 Seguro Popular clinics. These clinics are part of the Sistema de Protección Social en Salud in Mexico. Individuals who obtain health care at these clinics are covered by public health insurance (Seguro Popular), and the services they get for T2D care include medical visits, referrals to specialists and nutritionist when needed, laboratory testing, and free medicines. The medical visits include medication prescription, blood pressure management, lipid monitoring, and eye/foot care. Laboratory analyses vary from patient to patient but generally includes 3 annual tests of A1C, although other glucose, urine, and lipids tests are also available. Patients with complications are referred to specialized health centers.

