Participants will be randomized to a treatment condition in a 1:1 allocation ratio to one of the two treatment conditions using a computer-generated, block randomization procedure. Sequentially numbered opaque sealed envelopes will be used to conceal the allocation determination. The RA will inform participants about their treatment condition and protocol. After a group of 5 participants have been randomized to the *Yo Puedo!* + mHealth condition, the program will start. Within one week, participants will start the group sessions provided by the program instructors. The content and procedures in all sessions will be documented. Approximately 10% of sessions will be attended by one of the site Co-ls to evaluate protocol fidelity. The CHWs/MAs will remind participants about upcoming sessions at the end of a current session and will send a text or call participants the day before their next session. Attendance will be recorded. Written content from missed group sessions will be given to participants who will be asked to review at home and clarify questions with the program instructors. Follow-up data will be collected at 3 and 6 months.

At the end of the study, the program instructors, and select clinic personnel will be interviewed to identify successful and unsuccessful elements of implementing the protocol. Strategies for scale up will be identified. In addition, all participants will be interviewed upon completion of their 6 month data collection about their experience and satisfaction with the program. These interviews will be conducted by trained RA's who have not participated in any of the intervention protocol. We will carefully record any implementation issues.

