Efficacy data will be collected at the clinic by a trained RA, blinded to participant group assignment and includes clinical (A1C, BMI, WC, BP), T2D self-management, dietary intake, physical activity, and self-efficacy data. All of this data will be collected three times, at baseline, 2-3 months, and 6 month follow-up. We will also collect data on depressive symptoms and food security at all three data collection time points. *A1C* is our primary outcome and will be measured using standard disposable analysis methods. *BMI* will be calculated according to the formula, BMI = kg/m² using a calibrated electronic scale and a portable stadiometer. WC will also be recorded using standard measurement practices. *Systolic and diastolic BP* will be measured according to practice standards. Two readings separated by 1 minute will be averaged. We will also collect data on change in medical status, medication and dosage via the medical record.

Self-management will be measured by the Summary of Diabetes Self-Care Activities questionnaire, a multi-dimensional 12-item scale with items on general diet, specific diet, monitoring blood glucose, foot care, and smoking. Reliability and validity have been established in Spanish-speaking adults. This self-report questionnaire was used successfully in the initial *Yo Puedo!* study.

Dietary intake will also be evaluated by a one-day diet history. While there is no gold standard for self-report of dietary intake, the validity of Spanish dietary recall has been established. This diet history guide captures time, location, type of food and preparation, and amount consumed in past 24 hours. Calories, %fat intake, and fruit and vegetable intake will be calculated. We will

also assess diet intake with a brief modified version of a food frequency questionnaire which asks about how often a variety of foods was eaten in the past month, including culture specific foods. We will include a question regarding food label usage at the end of this questionnaire as the Yo Puedo curriculum teaches how to read food labels and emphasizes their use.

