Health information will be collected in a form which asks about any clinic visits, emergency room visits, episodes of hypoglycemia, diabetes-related health symptoms, medications, other health diagnoses, and A1C and blood pressure results in the previous 3 months. We will also collect data on participant demographics (age, gender, race/ethnicity, income) and depressive symptoms. We will use the Patient Health Questionnaire-8 (PHQ-8) to evaluate depressive symptoms, a well-established measure, with excellent reliability and validity in English and Spanish-speaking adults.

STATISTICAL ANALYSIS PLAN

To evaluate the preliminary efficacy of the program, initially the sample and variables will be described using frequency distributions and appropriate summary statistics. Additionally, the 2 groups will be compared to make certain that randomization procedures were adequate. If any baseline variables differ by group assignment, they will be included as covariates in subsequent analyses. The hypothesis that adults with T2D who receive the *Yo Puedo!* + mHealth will demonstrate better outcomes than adults with T2D in the control condition will be tested using Generalized Linear Mixed Models (GLMM) with an intent-to-treat analysis. While it is likely that significant main effects may not be found for all variables due to the sample size, identification of trends of significance (e.g., p<.10) and effect sizes will be possible. The results of analyses of the clinical outcomes of A1C and BP will require control for the impact of medication usage and dosage change (e.g., change in medications or dosage or no change, increased levels or not, and decreased levels or not).

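### The SAP names only main effects for its mixed model and leaves open both the follow-up contrast to be tested and whether baseline always enters; both can be fixed at no cost

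*Combined protocol and SAP*

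**What the plan says.** The Study Objectives and Design sections state the efficacy hypothesis as intervention "compared to the wait-list control condition at 3 and 6 month follow-up". On the efficacy outcomes, Design says: "All of this data will be collected three times, at baseline, 2-3 months, and 6 month follow-up". A1C "is our primary outcome and will be measured using standard disposable analysis methods".

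The Statistical Analysis Plan says that the hypothesis "will be tested using Generalized Linear Mixed Models (GLMM) with an intent-to-treat analysis". It does not list fixed effects, a visit term, a group-by-visit term, a covariance structure or the contrast to be tested. The only model effect it names comes in the next sentence, which begins "While it is likely that significant main effects may not be found for all variables due to the sample size" and goes on to say that trends and effect sizes can still be identified.

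Its one rule on baseline is: "If any baseline variables differ by group assignment, they will be included as covariates in subsequent analyses". It does not say whether the baseline value of an outcome is a response in the model, a covariate, or neither.

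**The concern.** The hypothesis is tied to two post-baseline visits, the data include a pre-treatment visit, and the analysis text links the two only through the phrase *main effects*. With three waves of data, an analyst could follow the SAP in several ways that answer different questions:

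- **Three waves as responses, group plus visit.** The group main effect averages in baseline, where randomisation makes the true difference zero.
- **Three waves as responses, group-by-visit, baseline as reference visit.** The coefficient labelled group is the baseline difference and carries no treatment information.
- **Follow-up waves only, baseline omitted because the groups look balanced.** The group effect is the right quantity, but the precision available from baseline is not used.
- **Follow-up waves only, baseline as covariate.** Nothing goes wrong, but the SAP's rule secures this only when the groups differ at baseline.

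Effect sizes are a stated product of this pilot, so the choice affects what is carried forward to a larger trial. Leaving it open also allows the contrast to be chosen after the data are seen.

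**Working it through.** The documents contain no power calculation or target effect, so there is no figure of the plan's own to reproduce.

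**Inputs from the documents.** The Design section describes a "pilot study design in which 60 adults with T2D are randomized", and "Participants will be randomized to a treatment condition in a 1:1 allocation ratio", so n = 30 per arm. There are three waves, and the hypothesis concerns the last two.

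**Assumptions.** Outcome SD 1 at each wave; equal correlation r between any two waves; effect d = 0.6 SD at both follow-ups; two-sided 5%; no dropout; power from the noncentral t with 58 df.

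**Expected value of the three-wave main effect.** With true differences 0, d3 and d6 and equal weights, it is (0 + d3 + d6)/3. For d3 = d6 = 0.6 this is 1.2/3 = 0.40, a loss of one third. Equal weights hold under equal correlation and complete data. The loss changes with the setting:

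- Measured against the 6-month effect, the estimate is one half of it if d3 is half of d6, and one third of it if d3 = 0.
- Under first-order autoregressive correlation of 0.5 to 0.8, the model's weights give 0.60 to 0.55 of d, a loss of 40% to 45%.

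**Variances.** Each is (2/30) × v. At r = 0.6:

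| Quantity tested | v | v at r = 0.6 | SE | Expected / SE | Power |
|---|---|---|---|---|---|
| Three-wave main effect | (1+2r)/3 | 0.733 | 0.221 | 0.40/0.221 = 1.81 | 43% |
| Follow-up average, no baseline | (1+r)/2 | 0.80 | 0.231 | 0.60/0.231 = 2.60 | 72% |
| Change to 6 months (plain group-by-visit) | 2(1−r) | 0.80 | 0.231 | 2.60 | 72% |
| Follow-up average minus baseline | (1+r)/2 + 1 − 2r | 0.60 | 0.200 | 3.00 | 84% |
| 6 months, baseline-adjusted | 1 − r² | 0.64 | 0.207 | 2.90 | 81% |
| Follow-up average, baseline-adjusted | (1+r)/2 − r² | 0.44 | 0.171 | 3.50 | 93% |

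Baseline-adjusted here means either baseline as a covariate or baseline as a response with the arms constrained equal.

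**Sensitivity to the correlation (power, d = 0.6).**

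| Quantity tested | r = 0.2 | 0.4 | 0.6 | 0.8 |
|---|---|---|---|---|
| Three-wave main effect | 61% | 50% | 43% | 37% |
| Follow-up average, no baseline | 84% | 78% | 72% | 67% |
| Change to 6 months | 44% | 55% | 72% | 95% |
| Follow-up average minus baseline | 55% | 67% | 84% | 99% |
| 6 months, baseline-adjusted | 65% | 70% | 81% | 97% |
| Follow-up average, baseline-adjusted | 86% | 87% | 93% | 99% |

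The baseline-adjusted average has the highest power in every column. Its gain over the unadjusted average is small at r = 0.2 (86% against 84%) and large at r = 0.8 (99% against 67%). The plain change to 6 months is worse than the three-wave main effect at r = 0.2 (44% against 61%), so the recommendation is baseline adjustment, not just any group-by-visit test.

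**Simulation check.** 200 mixed-model fits per model, with d = 0.5 and r = 0.7:

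- Group plus visit on three waves: mean estimate 0.311 (expected 0.5 × 2/3 = 0.333), rejection 24.5%.
- Group-by-visit with baseline as reference visit: group coefficient −0.018, rejection 4.5%.
- Baseline-adjusted follow-up model: mean estimate 0.488, rejection 90%.

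**The case against.** The strongest reply is that the sentence about main effects is a caveat on sample size and does not specify a model. It uses the plural, refers to all variables and does not contain the word group, so it may be informal wording for the intervention effect on each outcome. The hypothesis that the model is said to test is stated elsewhere in the same document as a comparison at 3 and 6 months, which points to post-baseline differences. If the responses are the two follow-ups only, the group main effect is the average follow-up effect and is not diluted. All of this stands.

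A reader might infer that the plan commits to a test diluted by a third, or to a test of the baseline difference. The documents do not support that. They never say that baseline is a response in the model, and nothing suggests that the analyst would read a baseline-visit coefficient as the treatment effect. Both outcomes are conditional risks of an open specification. The one-third figure itself needs equal wave weights.

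The reply does not supply the missing specification. If the phrase is loose wording, the SAP names no contrast at all. The baseline rule does not close the gap either: when baseline A1C looks balanced, the rule does not bring it in as a covariate, so it is then either a response or left out.

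**Conclusion.** The concern holds as an open specification with a clearly better and free alternative. The SAP does not name the between-arm contrast that answers its hypothesis at 3 and 6 months, and it does not ensure that the baseline value of the outcome is used.

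The consequence depends on how the model is fitted: attenuation if baseline is averaged in, no treatment information if the reference-visit coefficient is read, or lost precision without bias if baseline is dropped. The exact power figures rest on the assumed 0.6 SD effect, the assumed correlation and a two-sided 5% test. The advantage of the baseline-adjusted follow-up average held at every correlation tried from 0.2 to 0.8. It cannot be said that every group-by-visit contrast has more power than the main effect, because the ranking against the plain 6-month change reverses at correlation 0.2.

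For a 60-person pilot of feasibility and preliminary efficacy, whose SAP already expects some non-significant results, this is a free improvement and falls below must-fix.

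**What to change.** Replace the reference to main effects in the Statistical Analysis Plan with text such as:

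*The treatment effect is the between-arm difference at 3 months and at 6 months, estimated from a repeated-measures model with visit as a category and group-by-visit terms. The baseline value of the outcome always enters, either as a covariate or as a response with the arms constrained equal at baseline, and is never averaged into the group effect.*

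Choose one of the two baseline options in advance and report these contrasts, with confidence intervals, as the effect sizes. If a single summary is wanted, prespecify the baseline-adjusted average of the two follow-ups as well.

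The cost is two sentences and a few more model parameters. No extra data or visits are needed.

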Yo Puedo! Diabetes Self-Management Education + mHealth in Mexico City

NCT # 03159299

October 17, 2018

STUDY OBJECTIVES

- 1. To translate an evidence-based diabetes self-management education (DSME) program, Yo Puedo!, to the cultural norms, expertise of providers, and systems of care in Seguro Popular clinics in Mexico. The program will be adapted through a collaborative team of diabetes experts in the US and Mexico, Seguro Popular clinic administrators, physicians, nurses and adults with type 2 diabetes (T2D) in Mexico City, Mexico. This will include development and testing of a theory-based mHealth (pictorial text-messaging) component.
- 2. To evaluate the feasibility (process of implementation, fidelity of sessions, attendance, attrition), acceptability (interviews with program instructors, participants) and preliminary efficacy of Yo Puedo!+mHealth in adults with T2D in Mexico City. We will use a randomized, controlled pilot study design in which 60 adults with T2D are randomized to the Yo Puedo! + mHealth or a wait-list control condition with the hypothesis that clinical [A1C, body mass index (BMI), waist circumference (WC), blood pressure (BP)], T2D self-management, and self-efficacy outcomes will be greater in Yo Puedo!+mHealth participants compared to the wait-list control condition at 3 and 6 month follow-up. We also hypothesize that the Yo Puedo! + mHealth program is feasible and acceptable to adults with T2D and providers and that fidelity of the program will be maintained.

DESIGN

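### The SAP falls back on p<.10 trends and effect sizes but plans no confidence interval, although at 30 per arm a standardised difference is known only to about ±0.5 SD.

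*Combined protocol and SAP*

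**What the plan says.** Objective 2 and the Design section describe a pilot: "We will use a randomized, controlled pilot study design in which 60 adults with T2D are randomized". Under Interventions, allocation is equal: "Participants will be randomized to a treatment condition in a 1:1 allocation ratio". A1C "is our primary outcome and will be measured using standard disposable analysis methods". The hypotheses cover clinical, self-management and self-efficacy outcomes at 3 and 6 months.

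The Statistical Analysis Plan tests these with generalised linear mixed models under intent-to-treat. It then accepts that "it is likely that significant main effects may not be found for all variables due to the sample size", and names what remains available in that case: "due to the sample size, identification of trends of significance (e.g., p<.10) and effect sizes will be possible".

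The documents do not define the effect size and mention no confidence interval, standard error or precision target. They give no derivation of the 60, and no assumed SD, target effect, power or attrition rate.

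**The concern.** The sentence sets two things against each other: tests, which the sample may not support, and trends and effect sizes, which it will. An effect size can be calculated at any sample size, but its uncertainty comes from the same standard error that limits the test. If that standard error is too large for the test to detect an effect, it is also too large for the estimate to say how big the effect is. The plan gives the reader no figure from which to see this.

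Two things are at stake. First, preliminary efficacy could be reported as point effect sizes that are compatible with no benefit and with a large one, with nothing beside them to show it. Second, the p<.10 label works as a filter. Any estimate singled out for passing it is, on average, larger than the true effect, because the smaller estimates fail the filter. This differs from the false-positive rate of a p<.10 rule when there is no effect. It concerns imprecision and exaggeration when there is one.

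**Working it through.** **Inputs from the documents.** 60 randomised (Objective 2; Design), 1:1 (Interventions), so 60/2 = 30 per arm. The trend threshold is p<.10 (SAP), read here as two-sided because no sidedness is given. The 60 cannot be reproduced, since no inputs to it are stated.

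**Assumptions, because the documents give no figure.** Attrition 20%; correlation r of baseline with follow-up 0.5 to 0.7; A1C SD 1.5 to 2.0 percentage points; intraclass correlation 0.01 to 0.10 within the intervention groups of 5; true effects of 0.3, 0.5 and 0.8 SD. The 95% level is a convention.

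**1. Half-width of the 95% interval, in SD units.**
- Unadjusted, 30 per arm: SE = √(2/30) = 0.258; t(58 df) = 2.002; half-width 2.002 × 0.258 = 0.52.
- 20% attrition, 24 per arm: SE = √(2/24) = 0.289; t(46 df) = 2.013; half-width 0.58.
- Baseline adjustment, 30 per arm: multiply by √(1 − r²). At r = 0.5, 0.517 × 0.866 = 0.45. At r = 0.7, 0.517 × 0.714 = 0.37.
- Clustering in the intervention arm only (normal quantile): 1.96 × √[(1 + 4·ICC)/30 + 1/30] = 0.51 at ICC 0.01 and 0.55 at 0.10.
- For A1C: 0.37 × 1.5 = 0.55 up to 0.517 × 2.0 = 1.03 percentage points either side.

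**2. What an observed effect size would mean.** Exact noncentral-t 95% intervals at 30 per arm, unadjusted:
- observed 0.3 SD: −0.21 to 0.81
- observed 0.5 SD: −0.02 to 1.01
- observed 0.8 SD: 0.27 to 1.32

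**3. The trend threshold uses the same SE.** The smallest difference that reaches p<.10 is 1.672 × 0.258 = 0.43 SD.

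**4. Inflation of estimates that pass p<.10 in the favourable direction** (normal approximation, unadjusted). Mean estimate given selection = d + SE × φ(a)/[1 − Φ(a)], with a = 1.645 − d/SE.

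| Assumed true d | a | Mean estimate if p<.10 | Ratio to truth |
|---|---|---|---|
| 0.3 | 0.483 | 0.3 + 0.258 × 0.355/0.315 = 0.59 | 2.0 |
| 0.5 | −0.292 | 0.5 + 0.258 × 0.382/0.615 = 0.66 | 1.3 |
| 0.8 | −1.454 | 0.8 + 0.258 × 0.139/0.927 = 0.84 | 1.05 |

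With baseline adjustment the SE falls by the factor in step 1. At d = 0.3 the mean estimate becomes 0.52 (r = 0.5) or 0.45 (r = 0.7), a ratio of about 1.7 or 1.5.

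**5. Power of the 5% two-sided t test at 30 per arm**, for comparison: about 21% at 0.3 SD, 48% at 0.5 SD and 86% at 0.8 SD.

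**The case against.** The other side has a reasonable case, and parts of it stand.

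- A reader might infer that the plan calls the sample too small for significance. It does not. It says only that significance may be missed for some variables, and power is 86% at 0.8 SD.
- A reader might infer that the plan claims its effect sizes will be precise. It says only that they can be identified, which is true at any sample size. The gap is the missing statement of precision.
- A reader might infer that a later trial will be sized on these estimates and so be underpowered. The documents state no such use. Their aims are feasibility, acceptability and preliminary efficacy, with some attention to scale-up. Nor do they say that only results passing p<.10 will be reported. A ban on later use would forbid something not planned.
- A reader might take a doubling of the effect as a general property of this design. It holds only for an assumed 0.3 SD without adjustment.
- The mixed model, with a baseline and two follow-ups, may do better than the unadjusted figure. That is so, but the plan does not say that the baseline value of the outcome enters the model, and attrition or clustering works the other way.
- A mixed model prints standard errors routinely, and silence does not show that intervals would be withheld. That is fair, but the plan commits only to p-values and effect sizes.

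Pilot status does not answer the point. A pilot's efficacy results are read mainly as estimates, so their precision has to be shown.

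**Conclusion.** The concern holds as a gap in reporting and interpretation; it does not invalidate the design. The plan offers trends and effect sizes where tests may fall short, with no interval, and the shared standard error leaves those effect sizes uncertain by roughly 0.4 to 0.6 SD either way. The 0.52 SD figure needs only the stated 60 and 1:1 allocation, with all 60 analysed and no adjustment. The rest of the range depends on the assumed attrition and correlations.

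The inflation figures illustrate what happens if estimates are highlighted for reaching p<.10. They depend on an assumed true effect and are slight when that effect is large. The point does not rest on any use of the results in a later trial. It is a cheap improvement that should be made.

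**What to change.** Replace the SAP clause on trends and effect sizes with:

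> For A1C and each other hypothesised outcome, the adjusted between-group difference at 3 and 6 months will be reported in its own units with a 95% confidence interval, whatever its p-value; results will be interpreted from the interval and not described as trends. With 60 randomised, the expected half-width is about 0.4–0.6 SD depending on baseline correlation and attrition, so estimates are preliminary and imprecise.

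If a standardised effect size is reported as well, state how it is defined, including the SD used as its denominator.

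The change is to SAP wording only and needs no extra participants, visits or data. Its cost is that the pilot's stated ability to show efficacy becomes less favourable.

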Interventions. All participants will receive standard T2D care at a Seguro Popular clinic as described above. The wait-list control condition group will receive a handout on T2D self-management and the opportunity to participate in the *Yo Puedo!* + mHealth program at the completion of 6-month data collection. The *Yo Puedo!* + mHealth DSME program includes: a) six

interactive group-based sessions (plus an initial orientation session) led by the program instructors on T2D self-management that is culturally relevant and at a low health literacy level (*Yo Puedo!* protocol adapted for Mexican context; see Table 1); b) behavioral support to collaboratively problem-solve barriers to change; and d) empowerment-based strategies to facilitate provider-patient communication. The *Yo Puedo!* program will be supplemented by one way text messaging provided by a web-based platform with privacy and security rules, which allows for automated and personalized messages and a database to store all messages. Automated daily text messages will include messages to promote understanding of T2D self-management, self-efficacy, and adherence to self-management goals. All text messages sent will initially be stored in the text messaging platform but will be archived to the REDcap database for subsequent data analysis. Participants in this group will also receive blood glucose monitors and will be instructed on how to use them as a part of the instruction provided in the Yo Puedo curriculum. The in-person component will be 6 weeks; daily text messaging will be for 6 months.

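### The required control for medication change in the A1C and BP models means the arm coefficient need not be the total effect of assignment

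*Combined protocol and SAP*

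**What the plan says.** The STATISTICAL ANALYSIS PLAN section says that the efficacy hypothesis "will be tested using Generalized Linear Mixed Models (GLMM) with an intent-to-treat analysis". Baseline variables have their own rule: those that differ by arm become covariates. The section closes with a separate requirement: "The results of analyses of the clinical outcomes of A1C and BP will require control for the impact of medication usage and dosage change". The examples it gives are "change in medications or dosage or no change, increased levels or not, and decreased levels or not".

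Under DESIGN, the efficacy-data paragraph says that A1C "is our primary outcome and will be measured using standard disposable analysis methods", and it gives the source of the medication data: "We will also collect data on change in medical status, medication and dosage via the medical record". Efficacy data are collected at baseline, 2-3 months and 6 months. The plan does not say whether medication change is coded per visit or per participant. It neither limits the control to baseline medication nor names an A1C or BP model without the control, whether as primary or as a sensitivity analysis.

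**The concern.** A change in medication during follow-up happens after randomisation, and the documents describe ways in which assignment could influence it. All participants stay in standard clinic care, where visits include prescribing and blood pressure management (DESIGN, Setting and Interventions). The program adds "empowerment-based strategies to facilitate provider-patient communication", and for the program arm the Interventions paragraph states: "Participants in this group will also receive blood glucose monitors and will be instructed on how to use them". Medication change may therefore lie on the path from program to outcome. It may also mark poor control, if a high A1C or BP prompts the change.

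Conditioning on such a variable removes part of the effect that runs through prescribing, and it can also distort the comparison where prescribing responds to interim A1C. Intent-to-treat settles who is analysed. It does not settle what the arm coefficient means once a post-randomisation covariate is in the model.

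What is at stake is the pilot's main quantitative product. The plan concedes that significance may not be reached for every variable and says that "identification of trends of significance (e.g., p<.10) and effect sizes will be possible". The A1C effect size would depend on how prescribing differed between arms and on an unstated coding choice, and a reader could take it for the total effect of being offered the program.

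**Working it through.** There is no plan figure to reproduce. The sample of 60 carries no SD, effect size, power or alpha, and no medication-change rates are given. The finding rests on the text; the arithmetic below only illustrates it.

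**From the documents:** 60 participants, 1:1 (30 per arm), follow-up at 3 and 6 months.

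**Assumed:** baseline A1C SD 1.5; correlation of baseline with 3-month A1C 0.75 and with 6-month A1C about 0.6; direct program effect -0.3; effect of a medication increase -0.8; increases in 27% of controls and 42%, 15% or 27% of the program arm. Increases are either unrelated to 3-month A1C or triggered by it (log-odds slope 1.0 per A1C point).

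**Least squares on 6-month A1C, adjusted for baseline** (simulated, 400,000 per scenario). Let d be the program-minus-control difference in the proportion with an increase, and b the fitted medication coefficient.

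- Total effect = direct effect + (effect of an increase) × d
- Adjusted arm coefficient = total effect - b × d

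The fitted b is -0.80 when increases are unrelated to interim A1C. It is about -0.25 when high A1C triggers them, because the participants who receive increases started higher.

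| Increases, program vs control | d | Total effect | Adjusted, not triggered | Adjusted, triggered |
|---|---|---|---|---|
| 42% vs 27% | 0.15 | -0.30 - 0.80 × 0.15 = -0.42 | -0.42 + 0.80 × 0.15 = -0.30 | -0.42 + 0.25 × 0.15 = -0.38 |
| 15% vs 27% | -0.12 | -0.30 + 0.80 × 0.12 = -0.20 | -0.20 - 0.80 × 0.12 = -0.30 | -0.20 - 0.25 × 0.12 = -0.23 |
| 27% vs 27% | 0 | -0.30 | -0.30 | -0.30 |

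The shifts are 0.12 and 0.10 when not triggered, and 0.04 (9% of the total effect) and 0.03 (15%) when triggered.

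**Random-intercept mixed model on repeated visits, triggered increases** (simulated, 200,000 per scenario):

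- *Coded per visit:* b is -0.74 to -0.85. The shift runs from about 0.74 × 0.12 = 0.09 to 0.85 × 0.15 = 0.13.
- *Coded per participant, baseline A1C as covariate:* b is about +0.28 to +0.30, so the shift reverses direction. It is about 0.28 × 0.15 = 0.04 or 0.30 × 0.12 = 0.04 (-0.41 becomes -0.45; -0.20 becomes -0.16).
- *Coded per participant, baseline A1C as a response:* the arm-by-time term does not move. A flag that is constant within a participant drops out of a within-participant contrast when the data are balanced.

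**Scale.** Standard error of the arm difference: 1.5 × √(1 - 0.6²) × √(2/30) = 1.5 × 0.8 × 0.258 = 0.31; the simulated values were 0.28 to 0.31. The largest shift is 0.13/0.28 = 0.46 standard errors.

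**A second set of assumptions.** With no direct effect, increases in 50% vs 30% and -1.0 per increase, the total effect is -1.0 × 0.20 = -0.20. The adjusted coefficient is 0.00, or -0.08 if medication change and A1C share a cause. A benefit that works wholly through treatment change would be largely or entirely adjusted away.

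**The case against.** The strongest reply is that the harm may be nil. If medication change is one flag per participant, baseline A1C is a response and the test is the arm-by-time term, the estimate is the same with and without the flag. A rerun gave -0.424 both ways at 42% vs 27% and -0.200 both ways at 15% vs 27%. This stands for that model. The plan, however, speaks of main effects and fixes neither contrast nor coding, and other permitted models do move.

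The illustrated shifts are also small and rest on assumptions. With a 3-to-6-month A1C correlation of 0.8, the triggered least-squares coefficient is about -0.14 and the shift about 0.02. Medication decreases were not simulated. This is fair, and it limits any claim about size. It does not make the adjusted coefficient a total effect.

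The BP case is weaker. No BP scenario was computed, and glucose monitors offer no evident route to BP prescribing, which leaves the communication component. Neither component is said to target medication.

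Two readings would soften the point. Medication usage could include baseline use, for which adjustment is sound. The mixed-model sentence could also be read as a separate analysis without the medication term. But the listed examples are changes, baseline covariates already have their own rule, and the plan does not rank the two analyses.

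Finally, this is a pilot with no go/no-go rule tied to A1C, and the adjustment is declared openly. That limits the consequences, although the effect size is still what the pilot offers its readers.

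**Conclusion.** The concern holds. As written, the plan makes conditioning on what is most naturally a post-randomisation variable mandatory for the primary outcome and for BP, and it names no model without that control as primary. The arm coefficient may equal the total effect of assignment, for example if assignment does not alter medication change, but the plan gives no assurance of this.

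Size and direction cannot be derived from the documents. Under the main assumed inputs the A1C estimate moves by 0 to 0.13 points, always under half a standard error, so a significance verdict would seldom change. The problem is which effect is being estimated. It should be corrected before outcomes are compared, and the case is firmer for A1C than for BP.

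**What to change.** Replace the final sentence of the STATISTICAL ANALYSIS PLAN section with:

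> The primary A1C and BP comparisons are the GLMM in all randomised participants, without terms for medication change after randomisation. Adjustment for the baseline outcome and baseline medication is allowed if chosen before outcomes are compared. Medication change is reported by arm as an outcome. A model that adds medication change is exploratory, is labelled so, and states its coding (per visit or per participant).

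The cost is wording only: the medication data are already collected and the adjusted model is kept. The downside is that the primary estimate will include any effect that runs through treatment change, which must be said when results are reported. This text does not by itself settle the treatment contrast, the visit or whether baseline is a response or a covariate. Those are best fixed in the same revision.
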